4.3 Exclusion Criteria

All potential participants meeting any of the exclusion criteria at screening or study visits will be excluded from study participation. Male and female participants will be ineligible if they:

- Have a sensitivity or allergy to vaginal, anal, or rectal products,
- Have a sensitivity or allergy to any of the ingredients contained in the study products
- Have a sensitivity or allergy to sesame seeds
- Are HIV-positive at baseline, or have a known HIV-positive sexual partner,
- Have an active rectal or reproductive tract infection requiring treatment per current CDC guidelines or have other condition that, in the opinion of the investigator/study clinician, make the patient unsuitable for the study or unable to comply with study requirements (Note: HSV seropositivity without active genital lesions is not an exclusion criteria).
- Urinary tract infection (UTI).
- Have current inflammatory bowel disease (IBD) or history of active IBD within last 3 months,
- Have any other significant colorectal symptom(s) as determined by medical history, participant self-report, or physical exam (including but not limited to presence of any unresolved injury, infectious or inflammatory condition of the local mucosa, presence of symptomatic external hemorrhoids, and presence of any painful anorectal conditions that would be tender to manipulation),

- Have any other clinical condition or prior therapy that, in the opinion of the investigator/study clinician, would make the patient unsuitable for the study or unable to comply with the study requirements (including, as determined by medical history, participant self-report, or physical exam),
- Are unwilling to refrain from use of nonoxynol-9 (N9) for the duration of the study
- Are currently enrolled in other rectal or vaginal product studies
- Are unable or unwilling to communicate in English, or
- Are unable or unwilling to give written informed consent

Additional Exclusion Criteria for Female Volunteers:

- Are pregnant or breastfeeding. Pregnancy testing will be conducted at Visits 1-4 (screening and prior to any product use period)
- Have completed menopause (i.e., at least 12 months without menstrual periods)
- Are currently attempting to get pregnant or have an intention to get pregnant during their participation in the study
- Are unwilling to refrain from use of any vaginal product (inclusive of douching; exclusive of tampons during menses) other than study products
- Have clinically significant abnormal pelvic findings and/or findings requiring therapy as a function of clinical exam at Visit 1
- Report being within 30 days of their last pregnancy outcome or gynecologic surgical procedure

** Note: In cases where GC/CT is identified at screening, one re-screening after documented treatment will be allowed if the study timeline permits.*

4.4 Prohibited Medications and Procedures

Study participants will be advised not to use the following throughout study participation: any rectally or vaginally administered products containing N9, sex toys (broadly defined) (tampons during menses are allowed), or any other rectal or vaginal investigational products.

If participants report using any of these products while enrolled in the study, their study product provision will be put on hold, pending discussions with study site investigator, Sponsor, and/or DAIDS MO. Study staff will have a list of prohibited medications/procedures that will be used when actively reviewing concomitant medication and non-medicated OTC vaginal/rectal product use with the research participants during screening and throughout conduct of the study.

4.5 Required Medications and Procedures

Condoms are recommended for use by participants enrolled in this study and will be strongly encouraged for all sexual encounters during the study period. Natural oils can reduce the integrity of latex condoms: since both suppositories contain natural oil(s), the study will provide non-latex condoms to participants in quantities expected to be sufficient for the study period. These condoms will not be impregnated or coated with any type of spermicide. In the event that a participant needs additional condoms between visits, s/he may request these from the study at any time.

5. Study Product Regimen

The products will be evaluated by male and female participants during receptive anal intercourse (see Section 6.3, Formulation Evaluation) and vaginal-penile intercourse (females only). No product used in this study will include any anti-HIV compounds or drugs. During each of three study periods (between visits 2 and 3, 3 and 4, and 4 and 5), participants will evaluate one formulation. Each formulation will be

evaluated by each participant, namely: HEC gel, Zetpil® suppository, and Key-E® suppository. The ordering of product presentation will be randomized (see section 6.2 below). Participants will be blind to formulation (each product will be assigned a color and will be referred to as such, (e.g., ‘the orange product’; see §1.3.2). Study staff, including study clinicians and research staff, will not be blind to participant product assignments.

6. Study Procedures / Evaluation

See APPENDIX A: Schedule of Visits and Procedures

6.1 Overview

Volunteers will first enroll for STI/HIV/pregnancy screening and then, if eligible, for the Formulation Evaluation study activities. Once basic eligibility is determined (i.e., Visit 0, Prescreen; see section 6.1), potential participants will be scheduled for Visit 1 (See section 6.2 below). Name and other pertinent contact information (e.g., telephone number, address, email) for future confirmation or rescheduling of visit dates will be collected. At the first visit (Visit 1), staff will provide information about the visit, answer any questions, and obtain informed consent for those willing to participate in the screening process. Once consented, potential participants will be tested for STIs including HIV, and screened for any rectal signs or symptoms. Female participants will also be tested for pregnancy and screened for any vaginal signs or symptoms. If a participant meets the above eligibility criteria (with the exception of lab results) upon completion of Visit 1, and is still interested in participating, s/he will be tentatively scheduled for Visit 2, pending lab results. Once lab results are conveyed to the participant, and eligibility is confirmed, scheduling of Visit 2 will be confirmed. There is no minimum time requirement between V1 and V2. These visits will generally be scheduled approximately two weeks apart to allow for the processing and conveyance of lab results to the participant. If the participant does not enroll in Visit 2 within 30 days of completing Visit 1, s/he will be required to be re-screened (repeat V1) prior to Visit 2.

When an eligible and interested potential participant returns for Visit 2, staff will provide information about the remainder of the study, reconfirm eligibility (including a negative pregnancy test result for female participants), answer any remaining questions, and obtain informed consent. Once informed consent for the product evaluation portion of the study is obtained, the remainder of the study will proceed as detailed below (See section 6.3).

6.2 Recruitment and PreScreening (Visit 0)

Study volunteers will be recruited by methods common in the PI’s research, including advertisements (e.g., posters and street outreach), recruitment sessions at clinics and community-based organizations and events, internet/intranet advertisements and electronic social networking strategies (e.g., Lifespan Intranet, Craigslist, Facebook, GRINDR), the research team’s future studies contact list of previous participants who have given permission to be contacted for similar studies, and word-of-mouth from participants in various studies conducted by the PI and her colleagues. Initially, a volunteer will express interest in the study and, if necessary, provide her/his first name and telephone number and/or email for future contacts. Volunteers may contact staff by either calling the study phone number, emailing the study email account to arrange a time for prescreening, or completing the prescreener privately on location at a community-based site.

All interested volunteers will be assigned a Research Identification Number (RIN) as soon as contact with the study is initiated. Each RIN is only assigned once and never reused. Each volunteer will complete a brief prescreening questionnaire (Visit 0) administered verbally by study staff (either over the phone if interested individuals call in to the study office, or in person (and in private) if staff conduct recruitment activities at community organizations or events) (See APPENDIX: Questionnaire for Basic Eligibility: PreScreeners). Staff will read prescreening questions and potential responses aloud, and enter volunteers’

verbal responses into a secure prescreening computer database. Privacy during phone conversations will be established by the staff asking whether the volunteer is in a place where s/he can answer questions privately. Privacy for in-person prescreenings will be ensured by study staff having a quiet, private space arranged at the site. If volunteers feel at all uncomfortable with the privacy arrangements, staff will arrange for a phone prescreen to be conducted. Research staff will first describe study requirements and procedures, including risks, benefits, and compensation. Verbal consent for prescreening will be obtained prior to questioning. PreScreener questions have been piloted: administration times range between 15 and 25 minutes, with an average of 20 minutes per administration. If a volunteer meets all initial eligibility criteria s/he will be scheduled for Visit 1. No identifying information will be collected until the prescreening responses indicate initial eligibility (with the exception of first name and telephone number or email for rescheduling prescreening, if necessary). Once scheduled for V1, the volunteer's full name, address, and date of birth (necessary for clinic registration purposes), as well as contact information, will be collected in a separate file (not associated with the RIN-identified responses).

At any point in the prescreening process, an individual may choose to suspend the interaction for any reason. If this occurs, study staff will thank the individual for their time and interest and ask whether s/he would like to be included in a future studies contact log. The contact log is a password-protected database of individuals who are interested in our research and wish to be notified of future research opportunities. The information is not linked in any way back to a particular study. Only first name and preferred forms of contact (e.g., email or postal address, phone number) are maintained.

6.3 STI/HIV/Pregnancy Screening (Visit 1)

Once prescreening has been completed and a potential participant has met basic eligibility criteria, s/he will be scheduled for a clinical screening visit to be screened for STIs (N. gonorrhoeae, chlamydia trachomatis, and syphilis) and HIV (inclusive of pre- and post-test counseling), and (for female participants) pregnancy. Prior to any testing, staff will individually and privately provide information about the screening visit (Visit 1) and obtain informed consent. Participants will complete a brief CASI demographic survey.

A limited visual rectal exam will be performed on all volunteers (males and females) to screen for any rectal symptoms including lesions, chancroid, sores, ulcers, and warts. Laboratory specimens will be collected, including rectal swabs and urine for N. gonorrhoeae, trichomonas, and C. trachomatis by nucleic acid amplification, and serum for RPR testing to rule out syphilis. HIV testing will be done using a rapid HIV antibody test (e.g., OraQuick *ADVANCE*® Rapid HIV-1/2 Antibody Test) that detects antibodies to HIV-1 and HIV-2 in 20 minutes. (See APPENDIX B: HIV Testing Algorithm)

For female volunteers, a limited visual pelvic exam will be performed to evaluate for any mucosal lesions or ulcers (external genital exam). Pelvic examinations may be deferred during menses. A pregnancy test will be done on a urine sample using a standard pregnancy test kit (e.g., QuPID® Plus, Stanbio Laboratories).

Risk behaviors will be assessed and appropriate risk reduction goals established during standard HIV/STI counseling and testing discussions with all participants. Procedures follow the Rhode Island Department of Health (RIDOH) guidelines. HIV counseling and testing will be done either by clinical staff, or by non-clinical research staff who have been certified by the RIDOH as Qualified Professional Test Counselors (i.e., hold initial QPTC certificates and are in good standing). A risk reduction plan may include referral to additional services, as well as behavioral risk reduction goals tailored to the specific risks of the individual. In addition, all those who enroll in the study agree to follow the study guidelines noted in the Inclusion/Exclusion criteria (see § 4.3/4.4). If a participant is unable to adhere to the study guidelines, s/he may be withdrawn from the study.

Should an individual receive a positive test result for a curable STI, that individual will first be informed of the result by the study clinician or designee. After the individual has been informed, the participant will be referred to their primary care physician for treatment. If they do not have a primary care physician, they will be referred to the study clinician for treatment, who will follow CDC Recommendations for the Treatment of STDs. Once successfully treated, the participant can be rescreened for eligibility if they so choose. If a female participant has a positive pregnancy test, she will be referred via the study's clinician to appropriate care of her own choice, inside or outside the Miriam Hospital/Lifespan network.

6.4 Formulation Evaluation (Visits 2-5)

6.4.1 Randomization to Product Presentation Order

Once a participant has been successfully screened for STI/HIV and pregnancy and remains interested in participating in the study, s/he will be scheduled for Visit 2 and assigned to a randomized product evaluation order. There are 6 such orderings: (1) HEC, Zetpil®, Key-E®; (2) HEC, Key-E®, Zetpil®; (3) Zetpil®, HEC, Key-E®; (4) Zetpil®, Key-E®, HEC; (5) Key-E®, HEC, Zetpil® (6) Key-E®, Zetpil®, HEC). Approximately 3-5 participants (~2 males and ~2 females) will be randomly assigned to each possible assignment order. If, for any reason, the participant does not enroll in the study after randomization, their assigned product order will be re-assigned to another participant.

6.4.2 CASI Survey

After completing the Visit 2 informed consent process, participants will complete a CASI survey collecting relevant information on their sexual and reproductive health history.

6.4.3 Product Demonstration

After completing the Visit 2 informed consent process, study staff will acquaint the participant with the study product that s/he has been assigned to evaluate at home during the first product evaluation period. Staff will verbally review the insertion instructions for the assigned product, as applicable; if the HEC gel, study staff will also demonstrate how to insert the gel into the applicator using a demonstration applicator. If a suppository product, staff will verbally review the insertion instructions for the assigned product. Additionally, study staff will provide a condom use demonstration, noting important knowledge (non-latex, expiry date) to be considered, as well as step-by-step instructions for opening the condom wrapper, removing the condom, applying it (using an artificial phallus for the demonstration), and discarding a used condom appropriately. Any questions regarding the product insertion process, and/or correct condom use will be answered.

6.4.4 Product Provision

Following the demonstration(s), study staff will review the study procedures and guidelines with the participant and then provide the participant with two (2) doses of their assigned study product, and written instructions for inserting the product and using the condoms: the 2nd dose is provided only as a back-up, in case the 1st dose is dropped or sex does not occur after product insertion. All participants (male and female) will be instructed to use the study product during RAI at least once during the product evaluation period (~2 weeks). Female participants will also be instructed to use a separate dose of the suppository products for VI. When suppository products are provided, participants will be instructed to wait 15 minutes before rectal or vaginal intercourse to allow for product dissolution. Participants will be strongly encouraged to use condoms throughout the duration of the study (§4.5).

6.5 Data Collection

6.5.1 Phone Survey

Each participant will complete an automated phone survey (<3 min.) on a daily basis, which will capture data related to product use/nonuse behaviors and sexual behaviors. The automated system will call the participant every day at the same number and time (the number and time will be provided by the participant at V2, and can be updated upon participant request throughout the study as necessary). Daily phone surveys will occur every day starting the day the participant enrolls in the product evaluation study (V2) and continuing until Visit 5 has been completed, or they have/are withdrawn from the study. Collecting phone survey data daily will allow us to capture data on typical sexual behaviors, as well as any potential compensatory behaviors that can be queried during the IDI (e.g., changes in sexual activity, frequency, use/non-use of non-study products; see §6.5.3). If the participant does not answer the call from the automated system, a message will be left instructing the participant to call in to the phone survey system. If a participant does not complete a phone survey on a given day, the study team will be notified automatically by email and will then contact the participant to follow up.

The phone survey will capture basic variables that allow the survey system to prompt the user to complete a web-based survey when applicable, and to monitor for any adverse events or participant concerns. Following a report of RAI (and, for women, VI) in conjunction with study product use, participants will be prompted to complete a web-based survey regarding their experiences both with insertion of the product and in the sexual encounter. (See APPENDIX: Questionnaires: Daily Phone Survey).

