6.5.2 USPE Product Evaluation: Web-based survey

Web-based surveys (~30-45 minutes) will include USPE items and scales, conventional acceptability questions, and behavioral and psychosocial measures capturing participant experiences during RAI/VI (e.g., partner type; sexual behavior; product use self-efficacy; willingness-to-use product). Additionally, participants will be asked open ended questions about what they liked/didn't like about the product, and any other recommendations that they might have. These answers may be used to remind participants of salient experiences to be discussed further during the in-depth interview (IDI, see section 6.4). After completing the sex-associated web-based survey, participants will be prompted to schedule their next study visit. Following completion of the final questionnaire, participants will complete a face-to-face qualitative in-depth interview (IDI), with survey item evaluation elements as applicable.³² The IDI will focus on a discussion of the participant's use experience and the factors that impacted that experience, including product factors and the interaction of product experience factors and other use factors (timing of application, sexual behavior sequencing, etc). Data will be collected regarding participants' experiences of each of the salient dimensions of sensory perceptions and product characteristics. The web-based survey will include scales adapted to capture the RAI and VI experiences using suppository formulations. In addition, the web-based survey will include other items relevant to sexual behavior and prevention, such as partner perception items. The survey system presents each item and its potential responses as a separate screen. USPE items are divided into two sections: insertion/application experience and RAI/VI experience (as applicable). Remaining items are positioned before and after USPE sections, as applicable.

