7.1 Clinical Management of Adverse Events

7.1.1. General Adverse Events

By definition, an adverse event can be either a new finding or symptom, or a worsening of a pre-existing condition. In order to accurately capture adverse events in follow-up, all volunteers will be clinically screened, and a medical history obtained by the study clinician at V1, before enrollment in the product evaluation portion of the study. Adverse events (e.g., fever, pain) will be elicited during the daily phone survey and during study visits. Referral to appropriate care will be offered to participants as needed. Criteria for product hold for AEs, and for discontinuation of an individual's participation in the study are described below.

While the two OTC study products and the HEC placebo gel are overall considered safe, side effects or adverse events are possible and could occur in the context of any of the three product evaluations. Self-administration of study product could result in trauma to the anus, rectum, vagina, or genitals. In addition, side effects, including itching, burning, redness, rash or hives, are possible with any rectal or vaginal product use. Participants might also experience pain and/or discomfort during RAI/VI itself.

Should an adverse event or side effect be reported, study staff will first collect relevant information and contact the study clinician to determine whether the participant will be seen immediately or referred to her/his personal physician. If the event does not require immediate triage or treatment, study staff (or the study clinician) will discuss a plan, or any alternative referrals, and, if applicable, request that s/he sign a Release of Information form so that study staff can follow up on the event through resolution. Study staff will complete a follow-up phone call with the participant within 72 hours, to determine whether the event has been resolved, whether treatment was sought, what treatment was provided, and any other information that would 1) assure the participant has been properly treated, and 2) help to categorize the event for AE reporting purposes. Staff will continue to follow up with the participant until adequate resolution can be verified. If staff or the participant finds it necessary, referral back to the study clinician will be made promptly.

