7.4 Adverse Event Procedures and Reporting Requirements

7.4.1 Adverse Events Definitions and Documentation

An AE is defined as any untoward medical occurrence in a clinical research participant administered a study product and which does not necessarily have a causal relationship with the study product. As such, an AE can be an unfavorable or unintended sign (including an abnormal laboratory finding, for example), symptom or disease temporally associated with the use of a study product, whether or not considered related to the product. This definition is applied to all participants beginning from the time of first product use. The term “study product” for this protocol refers to HEC gel inserted with the HTI Comfort Tip® applicator, Key-E® suppository, Zetpil® suppository.

Study participants will be provided instructions for contacting the study site to report any untoward medical occurrences that they may experience, except for possible life-threatening events, for which they are instructed to seek immediate emergency care. Where feasible and medically appropriate, participants will be encouraged to seek evaluation at The Miriam Hospital, where the study clinician is based, and to request that a study clinician be contacted upon their arrival. With appropriate permission of the participant, whenever possible, records from all non-study medical providers related to untoward medical occurrences will be obtained for review. All participants reporting an untoward medical occurrence will be followed clinically until the occurrence resolves (returns to baseline) or stabilizes over a 72-hour period.

Study staff will record in source documents all AEs reported by, or observed in, enrolled study participants regardless of severity and presumed relationship to study product. For each study participant, AE documentation and reporting will be undertaken throughout the scheduled duration of follow-up.

Complete descriptions of all AEs will be entered in source documents, and will include:

1. AE term (i.e., the one term that best describes what occurred)
2. AE start and stop dates
3. Severity grade of the AE (see grading table information)
4. Study product(s) administered
5. Relationship of the AE to the study product(s)
6. Action taken regarding the study product(s)
7. AE outcome (e.g., recovered or resolved, not recovered or not resolved, recovered or resolved with sequelae, or unknown)
8. What seriousness criteria, if any, were met

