7.4.3 Adverse Event Reporting to DAIDS

The SAE Reporting Category, as defined in Version 2.0 of the DAIDS EAE Manual, will be used for this study. The study agents that must be considered in determining relationships of AEs requiring expedited reporting to DAIDS are: HEC gel, HTI Comfort Tip® applicator, Key-E® suppository, and Zetpil® suppository.

Requirements, definitions and methods for expedited reporting of Adverse Events (AEs) are outlined in Version 2.0 of the DAIDS EAE Manual, dated January 2010, which is available on the RSC website (<http://rsc.tech-res.com/safetyandpharmacovigilance/>). The DAIDS Adverse Experience Reporting System (DAERS), an internet-based reporting system, must be used for expedited AE reporting to DAIDS. In the event of system outages or technical difficulties, expedited AEs may be submitted via the DAIDS EAE Form. This form is available on the RSC website: <http://rsc.tech-res.com/safetyandpharmacovigilance/>. For questions about DAERS, please contact the NIAID CRMS Support at [contact].

AEs will be reported to the DAIDS Medical Officer within 24 hours of the investigator becoming aware of the event during the entire study duration for an individual subject (from study enrollment until study completion or discontinuation of the subject from study participation for any reason). Additionally, the Investigator of Record (IoR) or designee will log any and all adverse events to the DAIDS Medical Officer on a monthly basis, regardless of expectedness or relationship to study product use. Furthermore, the local IRB categorizes AEs and the relationship to study product as follows: 1) definitely related, 2) probably related, 3) possibly related, 4) probably not related, and 5) not related. The IoR or designee will report all AEs in categories 1 and 2 to the DAIDS Medical Officer as related to the study product. The IoR or designee will report all AEs in categories 4 and 5 to the DAIDS Medical Officer as not related to the study product. Additionally, all AEs in category 3, defined by the local IRB as possibly related, will require consultation with the DAIDS Medical Officer in order to determine if the AE is categorized by DAIDS as related or not related to the study product.

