After the protocol-defined AE reporting period, unless otherwise noted, only Suspected, Unexpected Serious Adverse Reactions (SUSARs) as defined in Version 2.0 of the EAE Manual will be reported to DAIDS if the study staff become aware of the events on a passive basis (from publicly available information).

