10.5 Risk/Benefit Statement

10.5.1 Risks

It is not expected that this trial will expose human subjects to unreasonable risk. The products used in this study are unlikely to cause side effects. However, unanticipated side effects including irritation, sensitivity, or allergic reactions may occur. None of the formulations contain anti-HIV compounds or drugs.

Discomfort or Injury due to Study Products or Procedures

Study Products. Participants will be asked to evaluate 3 study formulations: HEC gel, Zetpil® suppository and Key-E® suppository, none of which contain any anti-HIV compounds/drugs. Participants will be advised not to taste or ingest any of the products. The likelihood of risk due to allergy or sensitivity will be mitigated by asking all participants during study screening if they know or suspect that they are allergic to rectal or vaginal products of any kind, including lubricants, as well as all ingredients specific to the study products. Symptoms indicating general allergic reaction include: itching, burning/stinging, red or watery eyes, sneezing, runny nose, coughing, rash or hives, chest tightness, shortness of breath, or shock; symptoms indicating sensitivity to Zetpil® include nervousness, tremor, sleeplessness, nausea, loss of appetite. Symptoms typically appear within 12 to 36 hours after exposure. As symptoms can be serious, participants known to have rectal or vaginal product or lubricant allergies will be excluded from the study.

It is possible that participants will experience rectal/vaginal pain, discomfort, or trauma due to use of the HTI Comfort Tip applicator. To mitigate this risk, participants will be given detailed insertion instructions (including lubrication of the applicator) during the appropriate product provision visit. It is also possible that participants will experience rectal pain, discomfort, or trauma related to digital insertion of suppositories, including lacerations due to fingernails, hangnails, or jewelry. Participants will be provided with single-use non-latex gloves and encouraged to use these as they deem necessary when inserting the product digitally in order to minimize these risks.

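### Adverse event collection can close less than 36 hours after the last product use, so a new non-serious reaction to that product can go uncollected

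*Combined protocol and SAP*

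**What the plan says.** **How events are found.** Section 7.1.1: "Adverse events (e.g., fever, pain) will be elicited during the daily phone survey and during study visits". Section 6.5.1 starts the daily calls at Visit 2, "continuing until Visit 5 has been completed, or they have/are withdrawn from the study".

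**When the period closes.** Section 7.4.1: "AE documentation and reporting will be undertaken throughout the scheduled duration of follow-up". Section 7.4.3 sets the period for reporting to the DAIDS Medical Officer: "from study enrollment until study completion or discontinuation of the subject from study participation for any reason". After that, "only Suspected, Unexpected Serious Adverse Reactions (SUSARs) as defined in Version 2.0 of the EAE Manual will be reported to DAIDS", and only if staff learn of them passively.

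**When Visit 5 takes place.** Section 6.5.2: "After completing the sex-associated web-based survey, participants will be prompted to schedule their next study visit". The interview at Visit 5 then follows the final questionnaire. No minimum interval from last use is given. The roughly two weeks in section 3 is an expected average between product provision visits.

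**When reactions appear.** Section 10.5.1 lists symptoms of general allergic reaction and of Zetpil sensitivity, then says: "Symptoms typically appear within 12 to 36 hours after exposure".

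**When the AE window opens.** Section 7.4.1: "This definition is applied to all participants beginning from the time of first product use". Section 7.4.3 counts from enrollment.

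**The concern.** The protocol gives its own onset range for the reactions it expects, but the end of collection is tied to a visit and not to the last exposure. Someone who uses the third product, completes the survey and attends Visit 5 soon afterwards can leave before that range has run out. The same is true of someone who withdraws from the study shortly after a use. A non-serious reaction that starts after exit is not asked about, and it lies outside the DAIDS reporting period.

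At stake is exploratory endpoint 3 (sections 2.1.2 and 8.2.2), the cumulative frequency and severity of adverse events judged related to the suppository forms. The last product used can be observed for less time than the ones before it. Safety follow-up of the individual participant is affected in the same way.

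**Working it through.** The plan gives no figure to reproduce here, and no sample size or power statement depends on this point. The check compares the two windows and then counts which product is exposed to the shorter one.

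**Inputs**
- Stated onset range: 12 to 36 hours (10.5.1), so 36 − 12 = 24 hours wide.
- End of active collection: Visit 5 or withdrawal (6.5.1, 7.4.3).
- Minimum gap from last use to Visit 5: none stated (6.5.2).
- Product orders: six (6.4.1). Participants: 20 to 30 (section 3).

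**Step 1: when the gap exists.** Let *t* be the hours from last use to exit. If *t* is 36 or more, the stated range is fully observed. If *t* is below 36, part of it is not.

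**Step 2: how much of the range is lost at a given *t*.** As an assumption for illustration only, spread onset evenly over the 24 hours. The share of onsets after exit is min(1, max(0, (36 − *t*)/24)).

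| *t* (hours) | Calculation | Share after exit |
|---|---|---|
| 12 or less | at least 24/24, capped at 1 | 100% |
| 18 | 18/24 | 75% |
| 24 | 12/24 | 50% |
| 30 | 6/24 | 25% |
| 36 or more | 0/24 | 0% |

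These are shares of reactions with onset in the stated range, given *t*. They are not shares of participants. The documents say nothing about the distribution of *t*, so the overall share cannot be computed.

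**Step 3: which product is affected.** Each product comes last in 2 of the 6 orders, so a suppository comes last in 4 of 6. That is 20 × 4/6 = 13.3 to 30 × 4/6 = 20, or about 13 to 20 participants if all complete. This counts people whose last product is a suppository, not people who leave early. After the first and second products the calls carry on into the next period and normally pass 36 hours.

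**Step 4: whether another provision covers the time after exit.**
- The re-assessment at least two weeks after the final visit (7.4.2) is for serious or expedited events still continuing at exit, and for related or possibly related events that had worsened by then. A new event is neither.
- The follow-up call within 72 hours (7.1.1) follows an event already reported.
- The final evaluation attempted for those withdrawn (7.1.4) has no stated timing relative to last use.
- The instructions for contacting the site (7.4.1) depend on the participant volunteering the event.

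None of these actively looks for a new reaction after exit.

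**The case against.** The strongest reply is that short gaps may be rare. Before Visit 5 the participant must report the use, complete a long web survey and the final acceptability survey, and book a staffed visit of 1.5 to 2 hours. Visit 5 also elicits events, so anything that has started by then is caught. This stands as a reason to expect a small effect. It does not set a lower limit on the gap.

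The visit schedule is listed as an appendix but was not in the text reviewed. It may contain a visit window, so the absence of a minimum interval is established only for the body text.

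Some stronger readings are tempting, and the documents do not support them:
- **A percentage or head count of participants who leave too early.** The frequency of receptive anal intercourse in 4.1 and the visit spacing in section 3 say nothing about the time from last use to Visit 5. Any such figure would rest on an invented gap distribution.
- **Anyone who stops a product drops out of collection that day.** Section 7.1.4 keeps following people who discontinue product, with their permission and on the same schedule. The point concerns withdrawal from the study.
- **A late reaction can never be recorded.** The SUSAR restriction in 7.4.3 limits reporting to DAIDS. It does not govern site documentation or IRB reporting (7.4.4) of an event the participant volunteers.
- **The two start points give two counts for endpoint 3.** That endpoint counts only events judged related to the dosage form, and an event before first use cannot be related to it.

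Endpoint 3 is also exploratory, and no comparison of event rates by product or period is planned for it.

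**Conclusion.** The point holds in a limited form. Active collection and the DAIDS reporting period can both close inside the protocol's own onset range, and nothing in the text reviewed prevents this or makes up for it. The loss is confined to new non-serious reactions to the last product used, in participants whose exit comes under 36 hours after that use. Its frequency is unknown and may be small. The primary endpoints are unaffected.

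The conclusion rests on three conditions: the unseen visit schedule sets no minimum interval, the 12 to 36 hour figure applies to allergy and sensitivity symptoms and not to adverse events in general, and the word typically in 10.5.1 means that 36 hours is not an outer limit.

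The differing start points in 7.4.1 and 7.4.3 are a wording mismatch to reconcile, with no effect on endpoint 3.

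**What to change.** In 6.5.1 and 7.4.3, end AE collection and reporting at the later of (a) Visit 5 or withdrawal and (b) 36 hours after the last recorded product use. Keep the existing automated call running until then; after withdrawal, only with the participant's permission. If the visit-schedule appendix already sets a minimum interval of that length, citing it in these sections would be enough for those who reach Visit 5.

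Separately, use one start point for the AE window in 7.4.1 and 7.4.3, or state that one defines an adverse event and the other the reporting period.

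The cost is a wording change and one or two extra calls of under 3 minutes for those who exit early. A missed call would prompt staff contact, as it does now under 6.5.1. Calls are compensated at the next visit, so calls after Visit 5 need another payment route. No extra visit is needed. Because 36 hours is a typical and not a maximum onset, the change covers the stated range and not every later reaction.
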